Women will be followed from the time of enrollment through the rest of their antenatal course with delivery occurring no later than 40 weeks' gestation as per recommended for all women with A2 GDM per the American College of Obstetricians and Gynecologists. Delivery outcomes will be assessed through MyChart. There will be no special follow-up required postpartum for women who participate in the study. Following delivery, the CGM group will be asked to return their study devices. Additionally, both groups will be provided with a short survey regarding their perceptions of their blood glucose monitoring modality focusing on their preference for fingerstick monitoring versus CGM use and the ease of usability of the device during their pregnancy. Once the survey is completed, participation in the study will be over.

We hypothesize that women with A2GDM who are randomized to continuous glucose monitoring will have a lower incidence of the composite primary outcome, due largely in part to the ability to better track overnight glycemic control and adjust medications as needed to decrease the possibility of hyperglycemia overnight, as shown in the previous study using CGM in pregnancy, which will then decrease the incidence of adverse outcomes that are part of the composite primary outcome.

5. Genetic Testing N/A

- A. Describe**
 - i. the types of future research to be conducted using the materials, specifying if immortalization of cell lines, whole exome or genome sequencing, genome wide association studies, or animal studies are planned *Write here*
 - ii. the plan for the collection of material or the conditions under which material will be received *Write here*
 - iii. the types of information about the donor/individual contributors that will be entered into a database *Write here*
 - iv. the methods to uphold confidentiality *Write here*
- B. What are the conditions or procedures for sharing of materials and/or distributing for future research projects? *Write here***
- C. Is widespread sharing of materials planned? *Write here***
- D. When and under what conditions will materials be stripped of all identifiers? *Write here***
- E. Can donor-subjects withdraw their materials at any time, and/or withdraw the identifiers that connect them to their materials? *Write here***

- i. How will requests to withdraw materials be handled (e.g., material no longer identified: that is, anonymized) or material destroyed? *Write here*

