Inclusion Criteria: women between 18-50 years old, pregnant, diagnosed with gestational diabetes requiring medication (A2) during pregnancy

Exclusion Criteria: pregestational diabetes, diagnosis with gestational diabetes > 33 weeks gestation (too late in pregnancy for study enrollment due to proximity to delivery), anomalous fetus, fetal growth restriction during current pregnancy diagnosed prior to enrollment, abnormal diagnostic genetic testing or screening for the fetus, twin or higher order multiple gestation, non-compliance with prenatal visits (missing ≥3 visits prior to enrollment), maternal medical comorbidities (lupus, chronic hypertension, cancer, ischemic cardiovascular disease).

9. How will **eligibility** be determined, and by whom?

Eligibility will be determined by the PI and the study coordinator through chart review. The PI is the director of the Diabetes in Pregnancy clinic and oversees all patients that attend this clinic.

10. **Risks:** Describe the reasonably foreseeable risks, including risks to subject privacy, discomforts, or inconveniences associated with subjects participating in the research.

Risks to participating in the research include any risk associated with wearing the continuous glucose monitor. The sensor wires for the CGM go under the skin and the device is placed by the patient after instruction from one of our diabetes nurse educators. The device has been deemed safe for use by the FDA.

The standard of care is fingersticks and the CGM device is deemed to be as safe as fingersticks, which the patients will have been doing up until the point of enrollment.

Patients will be de-identified for data analysis.

There is no anticipated increased risk to the woman or her fetus for women in the CGM group compared to the standard monitoring group (with the glucometer and four times a day fingersticks) based on the use of the CGM alone. The risks to the pregnancy are related to the risks of developing gestational diabetes and are the same for women in the CGM arm and the control arm.

11. **Minimizing Risks:** Describe the manner in which the above-mentioned risks will be minimized.

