This protocol presents minimal risks to the subjects and Unanticipated Problems Involving Risks to Subjects or Others (UPIRSOs), including adverse events, are not anticipated. In the unlikely event that such events occur, Reportable Events (which are events that are serious or life-threatening and unanticipated (or anticipated but occurring with a greater frequency than expected) and possibly, probably, or definitely related) or Unanticipated Problems Involving Risks to Subjects or Others that may require a temporary or permanent interruption of study activities will be reported immediately (if possible), followed by a written report within 5 calendar days of the Principal Investigator becoming aware of the event to the IRB (using the appropriate forms from the website) and any appropriate funding and regulatory agencies. The investigator will apprise fellow investigators and study personnel of all UPIRSOs and adverse events that occur during the conduct of this research project through regular

study meetings and via emails as events occur after the events are reviewed by the primary investigator. The DSMB and IRB will be informed of the following adverse events within 5 days of the event becoming known to the principal investigator: intrauterine fetal demise, neonatal injury at birth due to large for gestational age, neonatal intensive care unit admission due to hypoglycemia or other complication from gestational diabetes, and maternal admission for hyperglycemia or hypoglycemia for other reason. The previously stated risks are not related to the use of CGM but are known risks of gestational diabetes. Risks related to the use of the CGM include the following: CGM device breaking causing need for professional assistance with removal, CGM malfunctioning resulting in admission for hypoglycemia or hyperglycemia.

13. Statistical Considerations: Describe the statistical analyses that support the study design.

Assuming an incidence in the standard monitoring group of 60% and an effect size of 40% with a power of 80% and an alpha of 0.05 we would need to recruit 134 women (67 per arm).

Approximately 140 women are diagnosed with gestational diabetes annually in our patient population. Around 50% of these will require medication and be diagnosed with A2 GDM that is around 60 patients annually eligible for recruitment.

SECTION II: RESEARCH INVOLVING DRUGS, BIOLOGICS, RADIOTRACERS, PLACEBOS AND DEVICES

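### The safety plan declares the listed maternal and infant events unrelated to CGM in advance, which conflicts with the trial's hypothesis and keeps most of them outside its own Reportable Event test

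*Combined protocol and SAP*

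**What the plan says.** Section I, 12 has three parts that bear on this point.

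- **Reportable Event.** The event must be serious or life-threatening, and either unanticipated or "anticipated but occurring with a greater frequency than expected) and possibly, probably, or definitely related". The same sentence adds a second category: "or Unanticipated Problems Involving Risks to Subjects or Others that may require a temporary or permanent interruption of study activities".
- **Listed events.** "The DSMB and IRB will be informed of the following adverse events within 5 days of the event becoming known to the principal investigator". The list is fetal demise, neonatal injury at birth due to large size, NICU admission for hypoglycemia or another complication of gestational diabetes, and maternal admission for hyper- or hypoglycemia, the last with the qualifier *for other reason*.
- **Attribution.** Directly after the list: "The previously stated risks are not related to the use of CGM but are known risks of gestational diabetes". The next sentence gives the risks that do count as CGM risks: device breakage needing professional removal, and "CGM malfunctioning resulting in admission for hypoglycemia or hyperglycemia".

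Section I, 1 defines the primary composite, which includes perinatal death, NICU admission for treatment of hypoglycemia, and birth trauma. Section I, 4 explains how CGM should act: overnight readings lead to medication adjustment, "which will then decrease the incidence of adverse outcomes that are part of the composite primary outcome". Section I, 10 states: "There is no anticipated increased risk to the woman or her fetus for women in the CGM group". It adds that the pregnancy risks are the same in both arms.

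**The concern.** Whether a device contributed to an event is normally judged after the event, from its circumstances. Here the answer is written down before any event occurs, for outcomes that the trial exists to compare between arms. If CGM readings can change these outcomes through medication, as the hypothesis says, the outcomes are not causally independent of CGM, and the safety plan cannot assume that they are.

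The attribution has a practical effect because relatedness is a required condition of the Reportable Event definition. An event already classed as unrelated cannot meet it, however often it occurs. If the listed events were more frequent in the CGM arm, the DSMB and IRB would receive them one at a time, each already described as a complication of gestational diabetes, with no stated count by arm that would reveal the pattern.

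**Working it through.** No arithmetic decides this point. The only nearby design figure is the sample size in Section I, 13 (134 women, 67 per arm). It does not enter the argument except as the number of women planned for the CGM arm. The check is a comparison of texts.

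**Step 1: the logic of the definition.** The parenthesis about excess frequency closes before the relatedness condition, so relatedness applies to both alternatives:

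Reportable Event = serious or life-threatening AND (unanticipated OR more frequent than expected) AND at least possibly related.

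If relatedness is answered *no*, the whole condition is false and the frequency term has no effect.

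**Step 2: apply it to each listed event.**

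| Listed event | Counterpart in the composite (Section I, 1) | Relatedness under Section I, 12 | Can it meet the test as written? |
|---|---|---|---|
| Fetal demise | Perinatal death | Declared unrelated | No |
| Birth injury due to large size | Birth trauma | Declared unrelated | No |
| NICU admission, hypoglycemia or other complication | NICU admission for hypoglycemia | Declared unrelated | No |
| Maternal glycemic admission, not attributed to malfunction | None | Declared unrelated | No |
| Maternal glycemic admission from CGM malfunction | None | Declared a CGM risk | Yes, if the other conditions hold |

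Three of the four listed types have a counterpart in the composite. The overlap is not exact: perinatal death is wider than fetal demise, and the listed NICU event is wider than the composite's.

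**Step 3: compare with the hypothesis.** Section I, 4 sets out a chain from CGM reading to medication change to composite outcome. The attribution sentence denies any link between CGM and the same kinds of outcome. Both cannot stand as general statements.

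**Step 4: does the protocol foresee wrong readings?** Yes. Section I, 4 provides for CGM and glucometer values that differ by more than 10 mg/dL at a clinic visit, and Section II (Devices, item 2) calls for a fingerstick check when symptoms occur. The possibility of an unfavourable link therefore comes from the protocol's own provisions.

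**Step 5: can the frequency term operate?** Section I, 12 gives no expected frequency for any listed event. The investigator's monthly safety review has no stated comparison by arm. Even with relatedness left open, nothing defines what counts as more than expected.

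**The case against.** The strongest reply is that the sentence does little harm, because other routes remain open. Much of this is right, and it rules out several stronger readings.

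- **An excess would go unreported, or could never lead to an interruption.** A reader might infer this, but the documents do not support it. Every listed event goes to the DSMB and IRB within 5 days whatever its relatedness. Section I, 12 lets the investigator or the IRB stop or suspend the study with no relatedness condition. The unanticipated-problem category has no written relatedness condition either. That category does not close the gap, though: it requires the problem to be unanticipated, the listed events are called known risks, and no exception for excess frequency is stated.
- **The next sentence contradicts the attribution for all listed events.** It does not. The overlap concerns maternal glycemic admissions only, and *for other reason* can be read as setting malfunction admissions apart. This is an ambiguity about one event type.
- **The trial would report no CGM-related serious events by definition.** This goes too far. Malfunction admissions and device breakage are expressly CGM risks.
- **The protocol predicts harm from CGM.** It predicts benefit, and Section I, 10 limits its statement to the use of CGM alone. The conflict is with causal independence.

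It can also be said that the sentence describes risks in general, and that the graded relatedness terms leave room for case-level judgement. That room exists, but the sentence supplies the answer for every event on the list, and nothing in the section tells the assessor to set it aside. The glucometer checks lower the chance of an undetected wrong reading. They do not justify ruling one out as a cause beforehand.

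Lastly, counts by arm could be seen as unplanned comparative looks, since three of the listed types overlap the primary outcome. That is a reason to keep the counts descriptive and with the DSMB.

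**Conclusion.** The concern holds in a limited form. The attribution sentence is a stated rule that conflicts with the hypothesis. As written, it takes the three infant event types, and maternal glycemic admissions not attributed to malfunction, out of the Reportable Event test even if they are more frequent in the CGM arm. The loss is in attribution and in seeing a pattern by arm. Notification of individual events and the authority to stop the study are unaffected.

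The conclusion rests on reading the sentence literally and on taking the list just before it as what it refers to. No event rates are assumed, and the documents give none from which to estimate how large an excess might be missed. The change should be made: the defect concerns outcomes central to the trial, and correcting it is cheap.

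**What to change.** 1. Delete the blanket attribution sentence from Section I, 12.
2. Record relatedness for each event case by case, using the CGM and glucometer readings available around it, without presuming the answer either way.
3. Add cumulative counts by arm to the notices already sent to the DSMB. State that the concurrent control-arm frequency is the reference for *expected* in the Reportable Event definition, and that the counts are descriptive.
4. State whether *for other reason* excludes admissions caused by CGM malfunction.
5. Reconcile the risk statements. Section I, 10 anticipates no added risk from CGM alone, Section I, 12 names malfunction admissions as a CGM risk, and Section II (Devices, item 2) lists infection and skin reaction, which the Section I, 12 list omits.

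The cost is protocol wording, one relatedness field per event and a short table. The small downside is that some events will be recorded as possibly device-related. No change to clinical management is involved.

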Women in the control group will continue to check their blood sugar levels as previously stated (fasting and 1 hour after eating) and use the MyChart Diabetes in Pregnancy log or paper log as they were using prior to requiring medication for the treatment of their diabetes. They will continue to be followed by the diabetes nurse educator and physicians in the Yale Maternal-Fetal Medicine clinic. Women who are randomized to the CGM group will also have their CGM data followed by the diabetes nurse educator and physicians in the Yale Maternal-Fetal Medicine clinic.

At the initial visit where the CGM is placed the reading on the device will be checked against a fingerstick value on a glucometer in clinic. This practice is then repeated at every clinic visit to ensure the device is calibrated correctly. If the blood glucose value between the CGM device and the glucometer differs by more than 10mg/dL the blood glucose will be rechecked with the glucometer using a different fingerstick. At this time if the blood glucose reading is still more than 10mg/dL different between the glucometer and the CGM the CGM sensor will be changed. If the sensor cannot reliably be confirmed with the glucometer at any clinic visit after following these steps the patient will be instructed to use her glucometer to monitor her blood glucose, as in the placebo group, and return to clinic in 1 week for attempted placement of the CGM again.

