- b) Documents pertinent information assigned to the investigational device (e.g., date, quantity, batch or serial number, expiration date if applicable, and unique code number): Documentation of the device lot numbers and expiration dates, date given to the study participant, number of sensors given and information for the participant on how to apply, change and troubleshoot the device will be kept in the research binder in the research room at [name] in the Yale Maternal-Fetal Medicine office.
- c) Stores the investigational device according to the manufacturer's recommendations with respect to temperature, humidity, lighting, and other environmental considerations: The devices will be stored in the research room in a locked storage area in the Yale Maternal-Fetal Medicine office at [name]. Per the manufacturer this device and sensor kits need to be stored at 39-77°F and between 10-90% humidity. The research room at the Yale Maternal-Fetal Medicine office meets these specifications for storage from the manufacturer.
- d) Ensures that the device is stored in a secure area with limited access in accordance with applicable regulatory requirements: The device and sensor kits will be stored in the research room in a locked storage area in the Yale Maternal-Fetal Medicine office at [name]. The people with access to the devices in this area will be research coordinators and the PI.
- e) Distributes the investigational device to subjects enrolled in the IRB-approved protocol: The Dexcom G6 continuous glucose monitor will be distributed to study participants at the time of randomization to women in the study group and will be applied in the Yale Maternal-Fetal Medicine office with the assistance of the diabetes nurse educator, study coordinator and/or physician in the clinic that day. Additional sensor kits will be distributed to patients at future office visits at the same location. Randomization will take place through an online enrollment randomizer (<https://studyrandomizer.com>).

SECTION III: RECRUITMENT/CONSENT AND ASSENT PROCEDURES

1. Targeted Enrollment: Give the number of subjects:

- a. Targeted for enrollment at Yale for this protocol: 134
- b. If this is a multi-site study, give the total number of subjects targeted across all sites: n/a

2. Indicate recruitment methods below. Attach copies of any recruitment materials that will be used.

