 Flyers	 Internet/web postings	 Radio
 Posters	 Mass email solicitation	 Telephone
 Letter	 Departmental/Center website	 Television
 Medical record review*	 Departmental/Center research boards	 Newspaper
 Departmental/Center newsletters	 Web-based clinical trial registries	 Clinicaltrials.gov
 YCCI Recruitment database	 Social Media (Twitter/Facebook):	
 Other:		

* Requests for medical records should be made through JDAT as described at
<http://medicine.yale.edu/ycci/oncore/availableservices/datarequests/datarequests.aspx>

3. Recruitment Procedures:

- a. Describe how potential subjects will be identified. Eligibility will be determined by the PI and the study coordinator through chart review. The PI is the director of the Diabetes in Pregnancy clinic and oversees all patients that attend this clinic.
- b. Describe how potential subjects are contacted. Potential subjects will be contacted while they are in the Diabetes in Pregnancy clinic either during their antenatal testing, diabetes nurse educator visit, ultrasound or clinic visit.
- c. Who is recruiting potential subjects? The PI, study coordinator and other members of the study team will recruit subjects.

4. Assessment of Current Health Provider Relationship for HIPAA Consideration:

Does the Investigator or any member of the research team have a direct existing clinical relationship with any potential subject?

Yes, all subjects

Yes, some of the subjects

No

If yes, describe the nature of this relationship.

Members of the research team also provide clinical care for the patients for management of their diabetes, prenatal care and delivery care.

5. Request for waiver of HIPAA authorization: (When requesting a waiver of HIPAA Authorization for either the entire study, or for recruitment purposes only. Note: if you are collecting PHI as part of a phone or email screen, you must request a HIPAA waiver for recruitment purposes.)

Choose one:

For entire study

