For a waiver of signed consent, address the following:

- Would the signed consent form be the only record linking the subject and the research? **YES** **NO**
- Does a breach of confidentiality constitute the principal risk to subjects? **YES** **NO**

OR

- Does the research pose greater than minimal risk? **YES** **NO**
- Does the research include any activities that would require signed consent in a non-research context? **YES** **NO**

Requesting a waiver of consent:

Screening only (*if for recruitment, the questions in the box below will apply to recruitment activities only*)

Entire Study

For a full waiver of consent, please address all of the following:

- Does the research pose greater than minimal risk to subjects?
 Yes *If you answered yes, stop. A waiver cannot be granted.*
 No
- Will the waiver adversely affect subjects' rights and welfare? **YES** **NO**
- Why would the research be impracticable to conduct without the waiver? Need to perform chart review to determine eligibility prior to consenting patients and the PI has an existing relationship with the patients eligible for participation in the study as she is the head of the Diabetes in Pregnancy Clinic at the Yale Maternal-Fetal Medicine office.
- Where appropriate, how will pertinent information be returned to, or shared with subjects at a later date?
Not applicable, requesting waiver for screening purposes only

SECTION IV: PROTECTION OF RESEARCH SUBJECTS

Confidentiality & Security of Data:

1. What protected health information (medical information along with the HIPAA identifiers) about subjects will be collected and used for the research?
We will look at additional variables within the subjects' protected health information including the patients': age, prior pregnancy and delivery history, BMI, medications during pregnancy, gestational age, antenatal admissions, ultrasound findings, maternal weight at delivery, maternal blood glucose values and neonatal weight at birth, APGAR scores and admission to the NICU.
2. How will the research data be collected, recorded and stored?

Patients' data within the Epic will be reviewed by only the researchers involved in this project. All data extracted from the electronic medical record will be stored with de-identified subject ID number-codes for later analysis. The data will be collected and stored in Yale Box on a Yale University password protected laptop.

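### Section 13 sizes the trial on an unadjusted two-proportion comparison and names no primary analysis; analysis by assigned arm, adjusted for two baseline covariates, would be a cheap improvement

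*Combined protocol and SAP*

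**What the plan says.** Section I, item 13 (Statistical Considerations) gives one sizing sentence and a recruitment estimate. The sizing inputs are "Assuming an incidence in the standard monitoring group of 60% and an effect size of 40% with a power of 80" percent and an alpha of 0.05, from which "we would need to recruit 134 women (67 per arm"). The enrolment target in Section III, item 1 is the same number: "Targeted for enrollment at Yale for this protocol: 134".

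Neither item 13 nor any other section names the primary test or model, the effect measure, the scale of the 40%, sidedness, the analysis set, covariates or a rule for missing outcomes. The hypothesis in Section I, items 1 and 4 is worded for women randomised to CGM and concerns the incidence of a binary composite.

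Two other places bear on the analysis. Under item 4 (Research Plan), if a CGM sensor cannot be confirmed against the glucometer, "the patient will be instructed to use her glucometer to monitor her blood glucose, as in the placebo group", and she returns in one week for another attempt at placement. Section IV, item 1 lists the data to be taken from the record. The list includes "age, prior pregnancy and delivery history, BMI, medications during pregnancy, gestational age" and also "maternal weight at delivery, maternal blood glucose values and neonatal weight at birth". It does not say when BMI or gestational age is taken.

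**The concern.** The implied analysis is a plain comparison of two proportions, with power already at the planning value and no reserve. Two things follow.

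First, choices that move the result are open. The test alone shifts power by about 5 points. The covariate list mixes values known before randomisation with values fixed afterwards, and birth weight is itself part of the composite (Section I, item 1). An adjustment chosen late could therefore use a post-randomisation variable or a component of the outcome. Women in the CGM arm who spend time on the glucometer have no stated place in the analysis.

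Second, the plan passes over a better method that it has the data to use. If baseline values predict the composite, adjusting for them adds precision without recruiting anyone.

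**Working it through.** **Inputs.** Control incidence 60%, effect 40%, power 80%, alpha 0.05 and 67 per arm come from Section I, item 13. Loss rates and covariate strengths are assumptions, because the documents give none.

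**1. Reproducing 134.** With p1 = 0.60, p2 = 0.60 × (1 − 0.40) = 0.36 and mean p = 0.48:

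n = [1.960 × √(2 × 0.48 × 0.52) + 0.842 × √(0.60 × 0.40 + 0.36 × 0.64)]² / (0.60 − 0.36)²

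= [1.3848 + 0.5772]² / 0.0576 = 3.8495 / 0.0576 = 66.8, so 67 per arm and 134 in total.

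Other readings do not give 134:

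| Reading | n per arm | Total |
|---|---|---|
| 60% vs 36%, two-sided, uncorrected | 67 | 134 |
| Same, continuity-corrected | 75 | 150 |
| Same, one-sided, uncorrected | 53 | 106 |
| 60% vs 20% (absolute 40 points), two-sided, uncorrected | 23 | 46 |

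**2. Exact power of the unadjusted comparison, 60% vs 36%.** This sums the binomial probabilities of all tables in which the test rejects.

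- 67 per arm, uncorrected chi-square: 79.4%.
- 67 per arm, Fisher's exact or continuity-corrected: 74.0% each.
- Uncorrected, averaged over assumed random loss of 2 / 5 / 10%: 79.4 / 78.1 / 76.0%.
- Larger effect, 60% vs 34%, at 67 per arm: 85.6%.
- Same 40% relative reduction from a control incidence of 50% or 40%: 65.4% or 51.7%.

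The uncorrected test is discrete and its size varies with n. At a common 48% incidence it is 0.055 at 60 per arm and 0.058 at 63 per arm.

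**3. Room for a model.** Expected events are 67 × 0.60 + 67 × 0.36 = 40.2 + 24.1 = 64.3, leaving about 70 women without an event. That supports arm plus two covariates.

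**4. Gain from adjustment.** Simulation used 20,000 trials per setting and marginal risks of 60% and 36%. The model was logistic with two baseline covariates, standardised to a risk difference, with a leverage-corrected (HC3-type) standard error and a t reference. The Monte Carlo error of each power is √(0.8 × 0.2 / 20,000), about 0.3 points. Entries are adjusted minus unadjusted power, in points.

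| Assumed AUC of the two covariates | 67 per arm | 60 per arm | 10% random loss |
|---|---|---|---|
| 0.50 (uninformative) | −0.3 | −3.0 | −2.0 |
| 0.64 (weak) | +1.8 | −0.8 | +0.3 |
| 0.71 (moderate) | +4.3 | +2.4 | +3.7 |
| 0.77 (strong) | +8.5 | +6.6 | +7.8 |

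With three covariates the gains at 67 per arm are slightly smaller: −1.2 / +1.1 / +3.8 / +7.7. In the weak case three covariates lose 1.6 points at 60 per arm and 0.4 at 10% loss.

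With both arms at 60%, type I error was 0.044 to 0.049 with the corrected standard error and 0.055 to 0.060 with the plain one.

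A separate simulation used a likelihood-ratio test, 3,000 trials per setting and 67 per arm. Adjusted against unadjusted power was 79% vs 79%, 83% vs 81% and 87% vs 79% at odds ratios of 1.0, 1.5 and 2.0 per SD for each covariate.

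**The case against.** The best case for the plan is that nothing in it is wrong. The 134 is reproduced exactly. The hypothesis, worded by randomised group, already points to comparison by assigned arm. An unadjusted chi-square by assigned arm would match the sizing and close the gap in one sentence. No document requires adjustment, no stratification factor is named, and every covariate strength above is assumed. All of this stands. It makes adjustment a recommended improvement and not the repair of an error.

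Some stronger readings are tempting but not supported:

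- *The 80% holds only at exactly 60% vs 36%.* It does not: power is 85.6% at 60% vs 34%. The limit is that the design has no margin for a smaller effect or for loss.
- *CGM women cross over for good.* Item 4 describes a temporary return to the glucometer, with re-placement to be attempted at one week.
- *The plan rules out covariates.* It is silent on them.
- *Adjustment costs 2 to 4 points at 60 per arm if the covariates are uninformative.* Part of that gap is the uncorrected chi-square's size of 0.055 there, against 0.044 to 0.049 for the adjusted test, so the comparison is not like for like.

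Loss may be small. The criteria exclude "non-compliance with prenatal visits (missing ≥3 visits prior to enrollment"), and "Members of the research team also provide clinical care for the patients for management of their diabetes, prenatal care and delivery care". But attendance before enrolment does not show that every delivery outcome will be captured, and item 4 says women are referred by their own primary provider. The loss rate remains unknown.

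**Conclusion.** The point holds as a cheap improvement. Section 13 rests on an unadjusted comparison and names no primary analysis, while the trial already collects variables that could sharpen it. At 67 per arm, adjustment for two baseline covariates changes power by about 0 to −1 point if they are uninformative, +2 if weak, and +4 to +8 if moderate to strong. These figures assume 60% vs 36% and the covariate strengths shown.

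A reader might infer that the sample size is wrong or that adjustment would make up for lost women. Neither follows. The 134 is correct for its stated inputs. With weak covariates the small gain can turn into a small loss once women are lost. Nor does adjustment remove the dependence on the 60% control incidence.

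**What to change.** In Section I, item 13:

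1. State the basis as 60% vs 36% (40% relative reduction), two-sided 0.05, if that is what is meant, and say that the 80% applies to 134 women with outcomes.
2. Name the primary analysis: women analysed by assigned arm, with CGM women temporarily returned to the glucometer counted in the CGM arm. Use logistic regression of the composite on arm plus two covariates chosen in advance and fixed before randomisation, for example BMI and gestational age, both taken at enrolment. Use no post-randomisation variable.
3. Report a standardised risk difference with 95% CI, which matches the two marginal proportions used for sizing. Use a small-sample-corrected standard error where practical.
4. Keep the uncorrected chi-square as the unadjusted supporting analysis, and note that its size can slightly exceed 0.05 at some sample sizes.
5. Say how missing outcomes are handled, and do not present adjustment as an offset for loss.

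The cost is a paragraph, two values recorded at enrolment, and a short prespecified script if the corrected standard error is used. No extra patients are needed. The price in power is 0 to 1 point at 67 per arm if the covariates prove uninformative, with a small loss also possible for weak covariates once women are lost.
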